#### **5.4.1.5. Troponin Evaluation and Stopping Criteria**

If post-screening, the local troponin is >Institutional ULN it is recommended that subjects undergo urgent evaluation of cardiac ischemia symptoms and ECG should be performed to rule out cardiac ischemia. An urgent repeat of troponin value and collection of sample for central lab evaluation should be obtained within 24 hours.

##### Asymptomatic subject:

If the second value of troponin is  $\leq$ ULN the subject can continue on study with close follow up of symptoms, ECG, and further troponin measurements as clinically indicated. If the second value of troponin remains >ULN treatment with belantamab mafodotin should be interrupted. The subject should undergo cardiac evaluation including ECHO testing for cardiac function. Any re-start of study treatment must be discussed with the GSK medical monitor who will consult with a member of the internal cardiotoxicity panel prior to restart. If the second value of troponin exceeds the threshold for MI according to local lab parameters, obtain cardiology consultation immediately. Permanently discontinue belantamab mafodotin and withdraw the subject from the study.

##### Symptomatic subject:

Obtain cardiology consultation immediately. Permanently discontinue belantamab mafodotin and withdraw the subject from the study.

#### **5.4.1.6. Valvular Toxicity Stopping Criteria**

Subjects who have a new asymptomatic, moderate regurgitation or stenosis by ECHO (Grade 2 mitral/tricuspid/aortic valvular toxicity per National Cancer Institute- Common Toxicity Criteria for Adverse Events [NCI-CTCAE], version 4.03, [NCI, 2010]) should temporarily discontinue study treatment and have a repeat evaluation by ECHO within 1 week. ECHO should be repeated every 1 to 2 weeks for 4 weeks or until valve recovery to baseline.

- If the valve recovers to baseline any time during the next 4 weeks after consultation and approval of the Medical Monitor, the subject may be restarted on belantamab mafodotin at a reduced dose(s). For such subjects, monitoring of the valve via ECHO will then be performed 2 and 4 weeks after rechallenge, and then per protocol.
- If repeat ECHO does not reveal valve recovery to baseline within 4 weeks, then the subject should permanently discontinue study treatment. The valve should continue to be monitored via ECHO every 4 weeks for 16 weeks or until resolution.
- Subjects with a Grade 3 or 4 **CCI** [REDACTED] valvular toxicity must discontinue study treatment. Valvular toxicity should continue to be monitored every 4 weeks for 16 weeks or until resolution. If recovery occurs (return to baseline via imaging AND symptom resolution) within 4 weeks, the subject may receive belantamab mafodotin at a reduced dose after consultation and approval of the Medical Monitor.

Echocardiogram must be performed as outlined in the Time and Event tables ([Table 7](#), [Table 8](#), and [Table 10](#)). Copies of all ECHO(s) and cardiology consultations performed on subjects who experience valvular toxicity will be required by GSK for review. Instructions for submitting qualifying ECHOs are provided in the SRM.

#### **5.4.1.7. Corneal Toxicity Stopping Criteria**

Corneal events should be graded according to the guidelines provided in [Appendix 9](#).

Subjects who develop Grade 4 corneal toxicity have to be discussed in detail between the treating ophthalmologist (or optometrist, if an ophthalmologist is not available), the GSK Medical Monitor, and possibly a GSK ophthalmologist, in order to determine whether the subject can be allowed to continue treatment with belantamab mafodotin, or should be permanently removed from study. If subject is allowed to continue on study, the dose of belantamab mafodotin will be reduced by 1 dose level. The decision will be documented in study files, together with individual assessment of risk-benefit. For details on re-start guidance, see [Table 4](#).

#### **5.4.1.8. Infusion-Related Reactions**

##### ***Infusion-Related Reactions Associated with Belantamab Mafodotin***

Premedication is not required prior to infusion of belantamab mafodotin unless deemed medically appropriate by the investigator following evaluation of infusion related reactions. Premedication should be considered in any subject who experienced an infusion related reaction at first or any subsequent infusion with belantamab mafodotin.

Infusion-related reactions should be managed by guidelines provided in [Table 4](#). A subject that experiences a Grade 4 IRR after belantamab mafodotin, should be permanently withdrawn from the study.

***Infusion-Related Reactions Associated with pembrolizumab***

If an IRR occurs during and/or after the infusion of pembrolizumab, refer to [Table 6](#) for further guidance.

**5.4.1.9. Allergic and Anaphylactic reaction stopping criteria**

All subjects will be monitored carefully for evidence of allergic response. A subject that exhibits signs or symptoms of severe hypersensitivity or anaphylaxis will receive appropriate medical treatment and be permanently withdrawn from the study.

Additional stopping criteria in case of significant toxicity are provided in Section [6.5.1](#)

**5.5. Subject and study Completion****5.5.1. Subject completion**

For Part 1 and Part 2, a subject is considered to have completed the study if they received at least 1 cycle of combination study treatment, and:

- The subject is followed until death, or
- The subject is followed until the end of study

The end of study is defined in Section [5.5.2](#). The end of study analyses will be performed at that time.

The eCRF should continue to be completed during the follow up period (every 3 months ( $\pm 7$  days) until the end of study. Please refer to [Table 10](#) for assessments to be completed during PFS follow-up visits or OS follow-up. OS follow-up data can be based on contacting subjects via phone calls/e-mails/or, other means of communication. Subjects who cannot be contacted will be considered lost to follow up. Follow-up data will be entered into the eCRF.

**5.5.2. End of Study Definition**

A final data cut-off will occur when all participants have either died, progressed, withdrawn consent, or have been followed for a minimum of 24 months from the LSFD.

Following 24 months post LSFD, PACT will be implemented. At this time, the collection of data for all recruited participants who no longer receive study treatment will stop entirely and clinical trial database will be closed. Those participants still benefiting from belantamab mafodotin will continue to receive study drug as assessed by the investigator, or can choose to discontinue belantamab mafodotin and only SAEs, overdose and pregnancy cases, and pre-specified ocular data will be reported directly to GSK.

Dispensing of study treatment following 24 months post LSFD, will utilize a manual resupply option, and drug accountability assessment will be performed at the site. All participants will be monitored and will receive follow-up care in accordance with standard local clinical practice. For participants who do continue to receive belantamab

mafodotin beyond the time of the final data cut-off, investigators will continue to report all SAEs, pregnancy and overdose cases up to 70 days after last dose of study treatment, and pre-specified ocular data (see SRM) will be reported until resolution unless the event is considered by the investigator to be unlikely to resolve, or the patient is lost to follow up. Additionally, any SAE and pre-specified ocular event that are ongoing at the time of this data cut-off must be followed up to resolution, unless the event is considered by the investigator unlikely to resolve, or the patient is lost to follow-up. GSK retains the right to request additional information for any patient with ongoing AE(s)/SAE(s) at the end of the study, if judged necessary.

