#### 7.3.1.1. Time Period and Frequency of Detecting AEs and SAEs

The investigator or site staff is responsible for detecting, documenting and reporting events that meet the definition of an AE or SAE.

All AEs will be collected from the time the first dose of study treatment is administered until 45 days following cessation of treatment regardless of initiation of new anticancer therapy.

All SAEs will be collected from the time the first dose of study treatment is administered until 45 days following cessation of study treatment. In addition, any SAE assessed **as related** to study participation (e.g., protocol-mandated procedures, invasive tests, or change in existing therapy), study treatment or GSK concomitant medication must be recorded from the time a subject consents to participate in the study up to and including any follow-up contact. All SAEs will be reported to GSK within 24 hours, as indicated in Section [7.3.1.7](#).

After discontinuation of study treatment, the investigator will monitor all AEs/SAEs that are ongoing until resolution or stabilization of the event or until the subject is lost to follow-up. At any time after 45 days the investigator may report any AE that they believe possibly related to study treatment.

Investigator is no longer required to review and approve SAEs in InForm within 72 hours of awareness of event. They will continue to record causality assessment for SAEs in source notes.

Following 24 months post LSFD, participants still deriving clinical benefit in the opinion of their treating physician may continue to receive belantamab mafodotin. For these participants, GSK will continue to collect safety information including SAEs, overdose and pregnancy cases and pre-specified ocular data via paper forms which will be reported directly to GSK. For these participants, SAEs, overdose and pregnancy cases will be

reported during the treatment period and for up to 70 days after last dose and pre-specified ocular data will be reported until resolution unless the event is considered by the investigator to be unlikely to resolve, or the patient is lost to follow up.

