### 7.3.2. **Pregnancy**

Do not collect pregnancy information for female subjects known to be pregnant during the screening phase or before exposure to study.

The need for a screening pregnancy test depends on whether a female subject is of childbearing potential or non-childbearing potential.

If a female subject is of childbearing potential, she must have a serum  $\beta$ -human chorionic gonadotropin ( $\beta$ -HCG) pregnancy test performed within 72 hours prior to the first dose of study treatment. Subjects with positive pregnancy test result must be excluded from the study. Subjects with negative pregnancy test result must agree to use an effective contraception method as described below during the study and for 4 months following the last dose of study treatment.

Details of all pregnancies in female subjects will be collected after the start of study treatment and for 4 months following last dose of belantamab mafodotin.

Details of all pregnancies for female partners of male subjects will be collected after the start of study treatment and 6 months following last dose of belantamab mafodotin.

If a pregnancy is reported, the investigator must inform GSK within 24 hours of learning of the pregnancy and must follow the procedures outlined in [Appendix 8](#).

Abnormal pregnancy outcomes (e.g., spontaneous abortion, fetal death, stillbirth, congenital anomalies, ectopic pregnancy) are considered SAE.

Pregnancy testing (urine or serum as required by local regulations) should be conducted at the end of relevant systemic exposure (4 months after the last dose of belantamab mafodotin) and correspond with the time frame for female subject contraception in Section [5.1](#).

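### The data stop at 24 months after the last subject's first dose contradicts the protocol's 45-day AE/SAE window and its 4- and 6-month pregnancy windows for subjects who stopped treatment shortly before closure

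*Protocol*

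**What the plan says.** Section 5.5.2 sets the timing: "Following 24 months post LSFD, PACT will be implemented". At that moment, "the collection of data for all recruited participants who no longer receive study treatment will stop entirely and clinical trial database will be closed". The synopsis, under its end-of-treatment and end-of-study definitions, says the same.

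The collection windows are set elsewhere:

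- Section 7.3.1.1 on AEs: "All AEs will be collected from the time the first dose of study treatment is administered until 45 days following cessation of treatment".
- Section 7.3.1.1 on SAEs: "All SAEs will be collected from the time the first dose of study treatment is administered until 45 days following cessation of study treatment".
- Section 7.3.2 on pregnancies in female subjects: "for 4 months following last dose of belantamab mafodotin". For partners of male subjects the period is 6 months. Appendix 8 repeats both.

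Section 5.5.2 also contains provisions that soften the stop:

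- For those who stay on belantamab mafodotin past the cut-off, "investigators will continue to report all SAEs, pregnancy and overdose cases up to 70 days after last dose of study treatment".
- For events already present, "any SAE and pre-specified ocular event that are ongoing at the time of this data cut-off must be followed up to resolution", apart from events thought unlikely to resolve and participants who can no longer be reached.
- A discretionary power for open events: "GSK retains the right to request additional information for any patient with ongoing AE(s)/SAE(s) at the end of the study".

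**The concern.** A site with a subject who took the last dose two weeks before closure has two instructions that cannot both be followed. One says collect every AE and SAE for another month. The other says collection for this subject has ended.

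The subjects concerned have just come off treatment, some of them because of toxicity. Section 6.5.2 itself warns that immune-related events may appear several months after the last pembrolizumab combination dose. The treatment of neighbouring cases is also uneven. A subject who takes one more dose after the cut-off has SAE, pregnancy and overdose reporting for 70 days. A subject who stopped a week before the cut-off has about a week of mandatory collection of new events. Safety is the primary objective of Part 1 and a secondary objective of Part 2, so completeness of this window matters to the report.

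**Working it through.** **Inputs.** 35 cycles maximum (Section 4.2.2); 21-day cycles (Section 4.2.1); closure 24 months after LSFD (5.5.2); 45-day AE/SAE window (7.3.1.1); 4- and 6-month pregnancy windows (7.3.2, Appendix 8). One month is taken as 365.25/12 = 30.44 days. Days are counted from the last-enrolled subject's first dose (day 0).

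**The plan's own figure.** 35 × 21 = 735 days, and 735/30.44 = 24.1 months. This reproduces the stated approximate 2 years.

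**Last dose against closure.** Dose 35 is given on day 34 × 21 = 714. Closure is on day 24 × 30.44 = 730.5. The interval is 730.5 − 714 = 16.5 days.

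**Windows for that subject.**

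| Window | Ends on day | Days past closure |
|---|---|---|
| AE/SAE, 45 days | 714 + 45 = 759 | 28.5 |
| Pregnancy, female subjects, 4 months (121.75 days) | 835.8 | about 105 |
| Pregnancy, partners, 6 months (182.6 days) | 896.6 | about 166 |

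The loss is 28.5 of 45 days, or 63% of the AE/SAE window. The end-of-treatment visit in Section 4.2.2 (30 ± 7 days after last dosing, days 737 to 751) also falls after closure. Table 10 note 2 allows it within 30 days, so it fits only if held early.

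**Who else is caught.** Any last dose after day 730.5 − 45 = 685.5 has a truncated AE/SAE window. For the last-enrolled subject this means cycle 34 (day 693, losing 693 + 45 − 730.5 = 7.5 days) or cycle 35. A subject first dosed d days before LSFD who completes 35 cycles on time loses 28.5 − d days, so d must be below 28.5. For female pregnancy the threshold is a last dose after about day 609, that is cycle 30 or later for the last-enrolled subject. A subject stopping for any reason in the 45 days before closure is caught too.

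**Rough number affected (assumption).** Time on treatment is taken as exponential, with the single-agent median PFS values in Section 2.2.5, 7.9 and 12.0 months, as its median. Placing all 40 subjects' first doses on the LSFD date, the expected number stopping between months 22.5 and 24 is:

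- median 12.0: 40 × (0.2726 − 0.2500) = 0.9
- median 7.9: 40 × (0.1389 − 0.1218) = 0.7

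On-time 35-cycle completers first dosed in the 28.5 days before LSFD are extra. Each such subject has a chance of about 0.13 to 0.26 of still being on treatment at 714/30.44 = 23.5 months.

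**Do the softening provisions close the gap?** The 70-day rule applies to subjects still on drug at the cut-off, including those who then choose to stop. It does not reach someone who stopped before. The follow-to-resolution sentence and the sponsor's right to ask for information concern events already ongoing. An event starting the day after closure, inside the 45 days, is covered by neither.

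**The case against.** The strongest reply is that safety reporting does not end with the database. Appendix 7 lets a site that hears of a new SAE after the electronic tool is off-line report it on paper or by telephone. Section 7.3.1.1 requires related SAEs to be recorded up to any follow-up contact, and allows an investigator to report a possibly related AE at any time after 45 days. Pregnancy is notified on its own form within 24 hours. Section 9.8 already accepts that follow-up differs between subjects. On this view only a one-sentence clarification is missing.

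Much of that stands. A reader might infer from the unqualified stop that corneal follow-up is cut short. The documents do not support this. Table 10 note 7 concerns subjects who already have decreased acuity or corneal signs or symptoms at the end-of-treatment visit. Section 5.5.2 follows ongoing pre-specified ocular events, and Section 6.12.3 continues follow-up of corneal findings present at end of study for up to 12 months. A reader might also infer that late SAEs must go unreported. They need not, because the paper and telephone route survives.

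What does not stand is that these routes replace the 45-day rule. The Appendix 7 route is permissive and limited to SAEs. Survival contacts under Table 10 end at end of study, so no scheduled contact remains to prompt a report. Non-serious AEs have no route for these subjects. The pregnancy form exists, but the period it serves is contradicted by the stop.

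**Conclusion.** The contradiction is real and narrow. Sections 5.5.2 and the synopsis conflict with 7.3.1.1, 7.3.2 and Appendix 8 on mandatory collection of new-onset AEs and SAEs, and of pregnancies, in windows still open at closure. It arises under the planned maximum treatment duration, with up to about 29 of 45 days lost for an on-schedule last-enrolled completer and more for anyone stopping closer to closure. Probably only a few of about 40 subjects are affected. The ORR analysis, about 15 months after the last subject's first visit, is untouched. It should be corrected because the correction is cheap and the loss falls on recently stopped subjects.

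Assumptions: closure exactly at 24 months after LSFD and on-schedule dosing. Delays can bring earlier-enrolled completers into the gap, while a delay of more than 16.5 days keeps the last subject on drug past closure and so under the 70-day rule. Section 5.5.2 is taken as governing, since Sections 4.2.2, 5.4, 5.5.1 and 9.7 refer to it. The synopsis still carries a 36-month end of study in two other places, under which on-schedule completers would not be truncated.

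**What to change.** In Section 5.5.2 and the synopsis, replace the unqualified stop with wording to this effect:

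- For a participant whose last dose precedes the 24-month point, AE and SAE collection ends when the 45-day window of Section 7.3.1.1 has run.
- The database is held open until then, and these events belong to the final safety dataset, so that they enter the AE tables. Paper forms sent straight to the sponsor after closure would not achieve that by themselves.
- After closure, SAE and pregnancy reporting for these participants continues directly to the sponsor by the paper route already set up for continued treatment, to the limits already stated (4 and 6 months for pregnancy).

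Section 7.3.1.1 should cross-refer to this. The same edit should reconcile the 70-day pregnancy reporting for participants continuing treatment with the 4 and 6 months of Section 7.3.2.

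Cost: one paragraph, closure up to about 45 days later, and paper forms for a few subjects. No endpoint, sample size or analysis method changes.

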### 5.5.3. Treatment after the End of Study

The investigator is responsible for ensuring that consideration has been given for the post-study care of the subject's medical condition whether or not GSK is providing specific post-study treatment. If a subject remains on treatment at the time end of study is achieved they may be offered an option to extend treatment.

## 6. INVESTIGATIONAL PRODUCT

The term of "Study Treatment" are used throughout the protocol to describe belantamab mafodotin and pembrolizumab as the investigational products (IP)

### 6.1. Investigational Products

Product name:	Belantamab Mafodotin	Pembrolizumab
[Formulation description:]	Solution containing 20 mg/mL, 1.5 mL/vial	Solution containing 100 mg/4 mL
Dosage form:	20 mg/mL solution for infusion Supplied as frozen liquid. Protect from light.	100 mg/4 mL solution that should be stored under refrigeration at 2-8°C (36-46°F). Protect from light. Do not freeze. Do Not Shake.
Unit dose strength(s)/Dosage level(s):	20 mg/mL, 1.5 mL/vial	100 mg/4 mL
Route of Administration	Delivered as IV infusion over at least 30 minutes. Infusions may be prolonged in the event of an infusion reaction. If subjects experience clinically significant infusion reactions, the infusion rate may be slowed for all future administrations of study treatment(s) for each subject. Should a global change in infusion rate be required, it will be communicated to sites in writing.	Delivered as 30 min IV infusion

Dosing instructions:	Dilute belantamab mafodotin solution in normal 0.9% saline to the appropriate concentration for the dose. See SRM for detailed preparation procedures.	Dilute pembrolizumab injection (solution) prior to intravenous Administration in 0.9% Sodium Chloride Injection, United States Pharmacopeia (USP) or 5% Dextrose Injection, USP. See SRM for detailed preparation procedures.
Manufacturer/ Source of Procurement:	GSK/Baxter	Merck

## 6.2. Medical Devices

Not applicable.

## 6.3. Treatment Assignment

Dose level allocation will be performed by GSK after subject has given written informed consent and has completed the necessary screening assessments. Eligible subjects will be enrolled to receive GSK2857916 at an assigned dose in combination with 200 mg of pembrolizumab.

Additional details are outlined in the SRM.

### 6.3.1. Study Treatment Administration

For belantamab mafodotin, please refer to the SRM for additional details on administration. For pembrolizumab, the study medical staff should make every effort to target infusion timing to be as close to 30 minutes as possible. However, given the variability of infusion pumps from site to site, a window between -5 minutes and +10 minutes is permitted (i.e., infusion time is 30 minutes -5 min/+10 min).

The Pharmacy Manual contains specific instructions for the preparation of the belantamab mafodotin and pembrolizumab infusion and administration of infusion solution.

#### 6.3.1.1. Belantamab Mafodotin Administration

Belantamab mafodotin will be administered to subjects intravenously as mg/kg calculated dose at the study site . The dose to be administered is based on actual body weight calculation, and may be reduced for toxicity according to protocol guidelines.

Administration will be documented in the source documents and reported in the eCRF. The time of start and end of infusion will be documented in eCRF.

Belantamab mafodotin will be administered over at least 30 minutes on Day 1 of each cycle at the assigned dose. Premedication is not required prior to infusion unless deemed medically necessary by the investigator, in which case it should be administered

according to institutional recommendations. In case of infusion related reactions related to belantamab mafodotin the rules outlined in Section [5.4.1.8](#) and in [Table 6](#) should be followed.

After the infusion of belantamab mafodotin has been completed subject will be required to enter at least 1 hour rest period before start of pembrolizumab infusion. In case of IRR during belantamab mafodotin infusion, subject needs to recover to Grade 1 or less in order to be able to receive pembrolizumab infusion.

